3.4. Baseline Variables

Full details on the covariates to be included in analyses are given in Section 5.2.4 and Section 5.2.5.

Baseline variables are age, gender, race, ethnicity, height, weight, body mass index, duration of diabetes. CCI

eGFR, systolic blood pressure, and diastolic blood pressure. Baseline variables are those collected on Day 1 prior to dosing or last measurement during screening visits before Day 1.

4. ANALYSIS SETS (POPULATIONS FOR ANALYSIS)

Data for all participants will be assessed to determine if participants meet the criteria for inclusion in each analysis population prior to unblinding and releasing the database and classifications will be documented per standard operating procedures.

Participant Analysis Set	Description
Enrolled/Randomly assigned to study intervention	"Enrolled" means a participant's agreement to participate in a clinical study following completion of the informed consent process. Potential participants who are screened for the purpose of determining eligibility for the study, but do not participate in the study, are not considered enrolled, unless otherwise specified by the protocol.
Safety	All participants randomly assigned to study intervention and who take at least 1 dose of study intervention. Participants will be analyzed according to the product they actually received.
PK concentration	All participants randomly assigned to study intervention who take at least 1 dose of study intervention and in whom at least 1 plasma PK concentration value is reported.
PK parameter	All participants randomly assigned to study intervention who take at least 1 dose of study intervention and who have at least 1 of the PK parameters of interest calculated.
CC I	

4.1. Treatment Misallocations

All analyses will be performed on an “as-treated” basis and will not include data from subjects who are randomized but not treated.

If a subject takes a treatment that is not consistent with the treatment they are randomized to, for example takes a treatment out of sequence or takes the same treatment twice, then they will be reported under the treatment that they actually receive for all safety, PK CCI analyses, where applicable.

4.2. Protocol Deviations

Subjects who experience events that may affect their PK profile (eg, vomiting) may be excluded from the PK analysis. At the discretion of the pharmacokineticist a concentration value may also be excluded if the deviation in sampling time is of sufficient concern or if the concentration is anomalous for any other reason.

A full list of protocol deviations will be compiled and reviewed to identify major and minor deviations prior to database closure.

4.2.1. Deviations Assessed Prior to Randomization

At screening, the investigator will assess subjects against the inclusion and exclusion criteria as set out in Sections 5.1 and 5.2 of the protocol.

4.2.2. Deviations Assessed Post-Randomization

Any significant deviation from the protocol will be reviewed prior to database closure and a decision taken regarding evaluation for each analysis population.

5. GENERAL METHODOLOGY AND CONVENTIONS

5.1. Hypotheses and Decision Rules

No formal inferential statistics will be applied to the safety, PK CCI data.

5.2. General Methods

All treatment arms of PF-06882961 and placebo will be reported separately.

5.2.1. Analyses for Continuous Endpoints

Continuous endpoints and relevant safety endpoints will be presented using summary statistics: number of observations, arithmetic mean, standard deviation, median, minimum and maximum values.

5.2.2. Analyses for Categorical Endpoints

Categorical endpoints and relevant safety endpoints will be presented using summary statistics: number of observations, counts and percentages.

[figure not shown]
[figure not shown]
5.2.3. Analyses of Time to event Endpoints

A Kaplan-Meier curve will be produced based on the time to the event of interest (starting from the time of start of dosing on Day 1) for each treatment separately and will be plotted on the same graph. No statistical testing for differences between treatment will be considered.

Details of censoring are included in Section 6.1.1.2.

CCI

CCI

5.3. Methods to Manage Missing Data

For the analysis of safety endpoints, the sponsor data standard rules for imputation will be applied.

5.3.1. Concentrations Below the Limit of Quantification

In all PK data presentations (except listings), concentrations below the limit of quantification (BLQ) will be set to zero. In listings BLQ values will be reported as “<LLQ”, where LLQ will be replaced with the value for the lower limit of quantification (LLQ).

5.3.2. Deviations, Missing Concentrations and Anomalous Values

In summary tables and plots of median profiles, statistics will be calculated having set concentrations to missing if 1 of the following cases is true:

1. A concentration has been collected as ND (ie, not done) or NS (ie, no sample),
2. A deviation in sampling time is of sufficient concern or a concentration has been flagged anomalous by the pharmacokineticist.

Note that summary statistics will not be presented at a particular time point if more than 50% of the data are missing.

5.3.3. Pharmacokinetic Parameters

Actual PK sampling times will be used in the derivation of PK parameters.

If a PK parameter cannot be derived from a participant’s concentration data, the parameter will be coded as NC (ie, not calculated). (Note that NC values will not be generated beyond the day that a subject discontinues.)

In summary tables, statistics will be calculated by setting NC values to missing; and statistics will be presented for a particular dose with ≥ 3 evaluable measurements.

If a subject receives a dose that was not assigned based on the randomized titration scheme, the data from that Day will not be included in any summary statistics but will be included in listings.

If an individual subject has a known biased estimate of a PK parameter (due for example to an unexpected event such as vomiting before all the compound is adequately absorbed in the body), this will be footnoted in summary tables and will not be included in the calculation of summary statistics or statistical analyses.

CCI

CCI

6. ANALYSES AND SUMMARIES

6.1. Primary Endpoint(s)

6.1.1. Adverse events

Adverse events will be reported in accordance with the sponsor reporting standards.

Incidence and severity of treatment emergent adverse event (TEAE) tables will additionally be produced ('All causality' and 'Treatment related', separately) to summarise the total number of adverse events by preferred term, which will be reported by treatment group (Placebo, 40 mg BID, 80 mg BID and 120 mg BID) and overall.

6.1.1.1. Hypoglycemia Monitoring

The hypoglycemic AEs will be listed in a separate table and summarized categorically by treatment as per Section [5.2.2](#).

6.1.1.2. Time to First Occurrence of AEs of Interest

Exploratory summaries on the time to the first occurrence of AEs of interest will be produced using Kaplan-Meier (KM) Curves as described in Section [5.2.3](#). Participants who discontinue from the study, discontinue from IP or initiate glycemic rescue medication prior to the start of the AE event of interest will be censored at the discontinuation/initiation date.

The three AEs of interest are: diarrhea, nausea and vomiting (based on preferred term). A separate KM plot for each AE will be produced separately.

Listings of AEs of interest will be produced.

6.1.1.3. Percentage of Participants with Ongoing AEs of Interest

Exploratory summaries on the percentage of participants reporting AEs of interest will be produced by week and treatment as per Section [5.2.2](#).

A line plot of the percentages over each week will be produced based on the summary statistics with a separate line for each treatment.

The AEs of interest are diarrhea, nausea and vomiting (based on preferred term); where a separate table and plot will be produced for each AE.

To calculate the percentage each week, the total number of participants who had not discontinued from the treatment prior to that respective week will be the denominator (note: if a participant did discontinue from the treatment during that respective week, they would be included in the denominator).

“Study Week” will be calculated using actual visit dates, rather than calendar days. For example, if vomiting occurs on Day 8 and Visit 2 occurs on Day 9 for a given patient, then the vomiting is considered to have occurred on Week 1 for this patient (Week 1 is Day1 to Day 8 for this patient).

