4. STUDY DESIGN

4.1. Overall Design

This is a Phase 1, randomized, double-blind (sponsor-open), placebo-controlled, 4-arm, parallel group study of PF-06882961 in adult Japanese participants with T2DM inadequately controlled on diet and exercise alone.

Participants will receive oral doses of PF-06882961 or placebo in this study. Approximately 9 participants will be enrolled in each arm, for a total of approximately 36 (4 arms) participants randomized. The randomization ratio will be 1:1:1:1 (1 of 3 active dosing regimens of PF-06882961 or placebo), and all 4 arms will be enrolled in parallel. The study will be conducted at a single clinical site in Japan.

Target dose levels, achieved after completion of titration, for the 4 arms of the study are placebo and PF-06882961 doses of 40 mg BID, 80 mg BID, and 120 mg BID. Dose titration will be incorporated to enhance tolerability to PF-06882961.

The maximum dose of PF-06882961 in this study will not exceed 120 mg BID.

Following the screening period to confirm eligibility (up to 4 weeks), the treatment period will be approximately 8 weeks, followed by an approximate 4-week follow-up. The total duration of participation in this study is approximately 12 weeks, not including the screening period. Dosing will occur with food BID, and up to 2 weeks (The target dose level: 40 mg BID), 4 weeks (The target dose level: 80 mg BID) or 6 weeks (The target dose level: 120 mg BID) of the 8-week dosing duration will be used for dose titration to maximize tolerability of PF-06882961, as depicted in [Figure 1](#) and [Table 3](#). Downward titration or dosing is not permitted during the study; participants who do not tolerate the titration scheme and/or assigned dose may be required to discontinue dosing of study intervention.

This study includes a total of 12 visits, of which 2 are inpatient study visits at the site and 7 are outpatient visits excluding screening to the site. The other visits are Follow-up visit and Follow-up telephone contact. Participants will be randomized at V2 to receive PF-06882961 or matching placebo for a duration of 8 weeks, with completion of dosing at V10. The inpatient stays at V2 and V10 consist of 4 days and 3 nights as listed in the [SOA](#). For the study duration between the inpatient study visits, participants will continue dosing with blinded study intervention provided in blister packs, either at home or at an outpatient visit to the study site.

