7. DISCONTINUATION OF STUDY INTERVENTION AND PARTICIPANT DISCONTINUATION/WITHDRAWAL

7.1. Discontinuation of Study Intervention

In rare instances, it may be necessary for a participant to permanently discontinue study intervention (definitive discontinuation). Reasons for definitive discontinuation of study intervention include the following:

- Criteria for a potential DILI (Hy's law) case are met (see [Appendix 6](#));
- Intent to become pregnant or pregnancy confirmed by serum β -hCG testing;
- Safety or tolerability concern arises, in particular if not responsive to symptomatic management, dosing with double-blind study intervention may be stopped in an individual participant at the discretion of the investigator.

If the criteria for permanent discontinuation are met, the site should notify the sponsor Medical Monitor or sponsor Clinician.

If study intervention is definitively discontinued, the participant will not remain in the study for further evaluation. See the [SOA](#) for data to be collected at the time of discontinuation of study intervention.

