8.3.1. Time Period and Frequency for Collecting AE and SAE Information

The time period for actively eliciting and collecting AEs and SAEs (“active collection period”) for each participant begins from the time the participant provides informed consent, which is obtained before the participant’s participation in the study (ie, before undergoing any study-related procedure and/or receiving study intervention), through and including a minimum of 28 calendar days, except as indicated below, after the last administration of the study intervention.

Follow-up by the investigator continues throughout and after the active collection period and until the AE or SAE or its sequelae resolve or stabilize at a level acceptable to the investigator and Pfizer concurs with that assessment.

For participants who are screen failures, the active collection period ends when screen failure status is determined.

If the participant withdraws from the study and also withdraws consent for the collection of future information, the active collection period ends when consent is withdrawn.

If a participant definitively discontinues or temporarily discontinues study intervention because of an AE or SAE, the AE or SAE must be recorded on the CRF and the SAE reported using the CT SAE Report Form.

Investigators are not obligated to actively seek AE or SAE after the participant has concluded study participation. However, if the investigator learns of any SAE, including a death, at any time after a participant has completed the study, and he/she considers the event to be reasonably related to the study intervention, the investigator must promptly report the SAE to Pfizer using the CT SAE Report Form.

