3.1.1. Adverse Events

An adverse event is considered treatment emergent (TEAE) relative to a given treatment if:

- The event starts during the effective duration of treatment (i.e. starting after the first dose but before the last dose plus lag time)

The effective duration of treatment is determined by the lag time. Any event occurring within the lag time, whether this occurs during a break in treatment or at the end of treatment, is attributed to the corresponding treatment period. The lag time is defined by the Pfizer Standard of 365 days post last dose of study intervention.

A 3-tier approach will not be used to summarize TEAEs due to small sample size.

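### The weekly nausea, vomiting and diarrhea percentages cover only participants still on treatment, so the curve can decline because intolerant participants leave; the numerator also needs an explicit rule

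*SAP*

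**What the plan says.** SAP 6.1.1.3 plans, for diarrhea, nausea and vomiting separately, a table and a line plot by study week and arm. The quantity is described this way: "Exploratory summaries on the percentage of participants reporting AEs of interest will be produced by week and treatment". The section heading calls these events ongoing; the text speaks of reporting them.

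The denominator is explicit: "the total number of participants who had not discontinued from the treatment prior to that respective week will be the denominator". A note adds that "if a participant did discontinue from the treatment during that respective week, they would be included in the denominator". No sentence says whether an event that starts or continues after treatment stops is counted.

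The dosing context is in the protocol. Table 3 in 6.1.1 raises the dose weekly until the target is reached, at Week 3, 5 or 7 depending on the arm. Protocol 6.6 permits no dose adjustment, and Protocol 4.1 says that "participants who do not tolerate the titration scheme and/or assigned dose may be required to discontinue dosing of study intervention".

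On data after treatment, Protocol 8.3.1 collects AEs "through and including a minimum of 28 calendar days, except as indicated below, after the last administration of the study intervention", and SAP 3.1.1 says: "The lag time is defined by the Pfizer Standard of 365 days post last dose of study intervention". Protocol 7.1 states: "If study intervention is definitively discontinued, the participant will not remain in the study for further evaluation". Protocol 7.2.1 instead keeps participants who ask to stop study intervention in the study and under follow-up.

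**The concern.** Tolerability of the titrated doses is part of the primary objective. Among the AE displays in SAP 6.1.1, this is the only one specified by week, so it is where a reader will look to see whether gastrointestinal events persist or fade as the dose rises. The TEAE tables are not specified by week, and the Kaplan-Meier curves show first occurrence only, with censoring when treatment stops.

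Within an arm, week and dose move together until the target is reached. If participants who feel unwell are the ones who stop, the later, higher-dose points describe a selected group. The curve then falls without anyone having adapted. Protocol 4.1 and 9.2 allow replacement of those who leave for non-safety reasons but make no such provision for safety leavers, so replacement does not offset this.

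The numerator is a second and separate matter. If events after treatment were counted while the participant was out of the denominator, the percentage would be too high. Two programmers following the same text could draw different trends.

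**Working it through.** The documents give no figure for this summary, so there is nothing to reproduce beyond the arm size: 4 arms × 9 = 36, which agrees with Protocol 4.1.

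**Inputs**
- n = 9 per arm (Protocol 4.1).
- x = participants with the AE at the start. This is assumed. The main case is x = 4 (44.4%), chosen near the 49.0% nausea in the earlier 28-day study (Protocol 2.2.2.1). That 49.0% is a cumulative incidence, so x = 4 may be high for a single week; x = 2 and x = 6 give a range.
- d = affected participants who have stopped before the week in question (assumed).
- Nobody who remains changes status.

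**Formulas**
- Starting value: x/n.
- SAP denominator, numerator drawn from the same participants: (x − d)/(n − d). This is below x/n whenever d > 0 and x < n.
- SAP denominator, numerator not restricted and the AE continuing after stopping: x/(n − d). This is always above x/n when d > 0 and x > 0.

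**Results, numerator from the same participants**

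| x | start | d = 1 | d = 2 |
|---|---|---|---|
| 2 | 2/9 = 22.2% | 1/8 = 12.5% | 0/7 = 0% |
| 4 | 4/9 = 44.4% | 3/8 = 37.5% | 2/7 = 28.6% |
| 6 | 6/9 = 66.7% | 5/8 = 62.5% | 4/7 = 57.1% |

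One affected leaver lowers the curve by 4.2 to 9.7 points.

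**Results, unrestricted numerator, x = 4:** 4/8 = 50.0% for d = 1 and 4/7 = 57.1% for d = 2. The curve rises. Under this reading the percentage can pass 100%: 8 affected, 2 of them stopped, gives 8/7 = 114%.

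**Does a fixed denominator cure the fall?** Not alone. With x = 4 and d = 2, counting leavers as event-free gives 2/9 = 22.2%, lower than the on-treatment 28.6%. Counting those who stopped because of the AE gives 4/9 = 44.4%, which removes the attrition effect.

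**How likely is stopping?** In the earlier study 6 of 98 discontinued, 2 of them for treatment-related TEAEs (Protocol 2.2.2.1). Treating these as independent per-participant rates in an arm of 9:
- At least one: 1 − (96/98)^9 = 17%; 1 − (92/98)^9 = 43%.
- At least two: 1% and 10%.
- At assumed rates of 10% and 20% for the longer 8-week course: at least one 61% and 87%; at least two 23% and 56%.

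The 6/98 rate includes leavers for any reason. Only departures of affected participants produce the fall.

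**The case against.** The strongest defense is that an on-treatment weekly percentage is a legitimate quantity and is openly defined. The participant stays in the denominator for the week of stopping, so the event that leads to stopping is not lost. The summary is labeled exploratory. The primary endpoint is TEAE incidence, tabulated by treatment group on the safety set, which keeps everyone who took a dose. SAP 5.2.2 requires n with categorical summaries, so shrinking numbers should be visible in the weekly tables. SAP 6.1.1.2 adds listings of these events and SAP 6.5.2 a discontinuation summary. All of this stands and limits the consequence. It does not put n on the plot or link stopping to the plotted AE.

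On the numerator, a percentage of participants ordinarily means a subset of its denominator. Study weeks are set from actual visit dates, so a participant with no further weekly visits has no obvious later week. Most analysts would fill the gap that way. This largely stands: the text is silent and does not prescribe an unrestricted numerator.

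A reader might infer that the unmatched numerator is what makes the curve fall. It is not: an unmatched numerator raises the curve, and a fall needs leavers to be out of the numerator too. A reader might also infer a dramatic distortion, for example with three of nine stopping for nausea. The documents do not support that. At 2/98 or 6/98, three or more of nine has a probability of about 0.07% or 1.5%. That study was shorter and randomized 3:1 to active drug or placebo, so higher rates are possible here, but no document gives one.

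Finally, a line that carries stoppers as affected has its own bias, because it cannot show nausea resolving off drug. That is correct, and it is why such a line can only supplement the on-treatment one.

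**Conclusion.** The point holds in a limited form. The on-treatment curve can decline through selective departure, and with about 9 per arm a single affected leaver is visible: 44% to 38%, or to 29% with two, when 4 of 9 were affected. These counts are illustrative. The effect rests on leavers being those with the event, on their no longer being counted after stopping, and on no change in those who remain.

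The missing numerator rule is a smaller matter of specification with the opposite sign. Whether it has any effect depends partly on whether events after treatment are recorded, which Protocol 7.1 and 7.2.1 leave in conflict.

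The documents do not support the inference that the trial's safety conclusions are biased. The TEAE tables keep participants who stop, and no inference or decision rule rests on this plot. What is at stake is how one exploratory figure is read. The change is worth making because it is cheap.

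**What to change.** In SAP 6.1.1.3:

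1. State that the numerator is those members of the week's denominator who have the AE present on at least 1 day of that study week, and align the heading and text on ongoing versus reporting.
2. Keep the on-treatment line. Show on the plot, for each week and arm, the n and the cumulative number who stopped treatment because of that AE.
3. Add one exploratory sensitivity line per arm with all dosed participants as the denominator, labeled *AE present or stopped treatment because of that AE*. Say how a participant who stops for two of the three events, or for another reason, is counted.
4. State the limit of that line: it is a composite, participants who stopped stay counted even if the event resolves, and it does not replace the on-treatment line.

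Separately, Protocol 7.1 and 7.2.1 must be reconciled on whether participants who stop treatment remain in the study.

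The cost is a few sentences of SAP text, modest programming and a busier figure.

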6.1.2. Electrocardiograms

Absolute values and changes from time-matched baseline for the ECG parameters QT interval, heart rate, QTcF interval, PR interval, and QRS complex will be summarized by treatment and time using sponsor reporting standards. Tables will be paged by parameter. Baseline is as defined in Section 3.1.2.

Mean change from time-matched baseline in ECG parameters will be plotted against day (for Day 1 and Day 56). On each plot there will be 1 line for each treatment. Corresponding individual plots of change from time-matched baseline will also be produced for each treatment.

Maximum increase from time-matched baseline for QTcF and heart rate will be summarized by treatment, according to sponsor reporting standards.

ECG endpoints and change from time matched baseline (QTcF, PR and QRS) will also be summarized descriptively by treatment using the following categories. Numbers and percentages of participants meeting the categorical criteria will be provided. All planned and unplanned post-dose time-points will be counted in these categorical summaries. All values meeting the criteria of potential clinical concern will be listed.

Table 5. Categories for QTcF Assessment

Degree of Prolongation	Mild (msec)	Moderate (msec)	Severe (msec)
Absolute value	>450-480	>480-500	>500
Increase from baseline		30-60	>60

Table 6. Categories for PR and QRS Assessment

Parameter	Criteria	
PR (ms)	max. \geq 300	
PR (ms) increase from baseline	Baseline >200 and max. \geq 25% increase	Baseline \leq 200 and max. \geq 50% increase
QRS (ms)	max. \geq 140	
QRS (ms) increase from baseline	\geq 50% increase	

Listings of subjects with any single post-dose value >500 msec will also be produced for QTcF.

The time-matched double differences in QT interval, heart rate, QTcF interval, PR interval, and QRS complex measures obtained following the Day 1 treatment, as defined in Section 3.1.2, will be summarized (N, mean, 90% confidence interval) for each treatment and time point.

Mean time-matched double differences in ECG parameters will be plotted against time postdose for Day 1 and Day 56 separately. On each plot there will be 1 line for each treatment and a single line for the placebo group(s). Corresponding individual plots of time-matched double differences will also be produced for each treatment.

The time matched double differences in QTcF will be plotted against PF-06882961 concentration. This will be a scatter plot for all observations where QTcF and drug concentration are recorded. Placebo data will also be included (with drug concentration set to zero). Different symbols will be used for each treatment.

